7.8. Blood Pressure Measurement

Concurrently, blood pressure assessments will be conducted on the day of blood sampling. The protocol for conducting blood pressure tests is outlined as follows:

- a. Participants are asked to rest for 5 minutes before blood pressure measurement without talking during the rest period.
- b. Participants are asked to sit upright with their back against the chair, ensuring that both feet are flat on the floor.
- c. Blood pressure measurement will be taken in a sitting position with the sleeve of the shirt open.
- d. The sphygmomanometer is placed on the right or left arm approximately 3 cm above the elbow crease. The arm cuff should not be too tight or too loose.
- e. The start button on the sphygmomanometer monitor is pressed. Blood pressure measurements will be taken three times, with a 1-minute interval between each measurement.
- f. The systolic and diastolic pressure results are recorded.

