3.2. Research objectives

The objectives of this study are:

1. Determine the effect of white tea consumption on the anthropometry of healthy subjects based on body weight, body mass index (BMI), waist circumference, and blood pressure.
2. Determine the effect of white tea consumption on biochemical parameters in healthy subjects based on blood sugar levels, complete lipid profile (total cholesterol, low-density lipoprotein, high-density lipoprotein, and triglycerides), liver function activity (based on liver enzyme function including alanine aminotransferase and aspartate aminotransferase), and kidney function (through measurement of creatinine levels, estimated glomerular filtration rate, and urea nitrogen levels).
3. Determine the effect of white tea consumption on hematology profile parameters associated with anaemia, including total red blood cell count, haemoglobin, haematocrit, mean corpuscular haemoglobin (MCH), and mean corpuscular volume (MCV).
4. Determine the effect of white tea consumption on the first line antioxidant enzymes activity of healthy subjects, such as superoxide dismutase, catalase, and glutathione peroxidase.

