7.5. Respondent Monitoring

Monitoring of anthropometry and blood pressure

The subjects of the research will undergo physical monitoring, including weight, height, BMI, waist circumference and blood pressure, by research team on days 0 and 15 (one day before and one day after the last day of the white tea intervention).

Laboratory monitoring

Laboratory monitoring was conducted on days 0 and 15 (one day before and one day after the last day of the white tea intervention) on blood samples from subjects in order to determine the effects of drinking tea for a period of 14 days. Should the preliminary investigative results pertaining to haematological parameters (RBC, HB, HCT, MCV and MCH), ALT, AST, serum creatinine levels, eLFG and urea nitrogen levels demonstrate abnormality, the subject will be withdrawn from the study for reasons of safety. Haematological tests are performed to ensure that the subject is not anaemic. ALT and AST tests are performed to ensure that there is no liver dysfunction, while serum creatinine, eGFR, and urea nitrogen tests are performed to ensure that the subjects do not have kidney dysfunction. In summary, the parameters employed in this study to observe the effects of white tea consumption are outlined as follows:

- a. Hematology profile
- b. Lipid profil
- c. Fasting blood glucose
- d. ALT dan AST
- e. Serum creatinine level, urea nitrogen level and eGFR
- f. First line antioxidant enzymes (SOD, CAT dan GPx).

Monitoring consumption and daily activities

In order to ensure that respondents adhere to the prescribed dietary regime, researchers will ensure that subjects abstain from the consumption of particular products that must be avoided during the course of the research process. Researchers will record all food and beverages consumed, the subjects' daily activities, and any complaints that may be experienced by the subjects, whether related or unrelated to the administration of white tea products.

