8. STATISTICAL ANALYSIS

The mean data before and after treatment will be tested for homogeneity and normality. In order to draw parallels between the two data sets, parametric measurements will be considered using the T-test for data with normal distribution, while data with abnormal distribution will be analyzed using a non-parametric test, namely the Wilcoxon test. The statistical analysis of all data will be conducted using SPSS version 20.0.

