APPENDIX 1. SCREENING FORM FOR SUBJECTS

SAMPLE

Research Number:	Respondent's initials: [] [] []
------------------	------------------------------------

SCREENING 1 – PERSONAL DATA

PERSONAL DATA		Officer ()
Date of data collection	: [] / [] / [] (DD/MM/YY)	
Name / initial	: [] [] []	
Place and Date of Birth		
Age	: Tahun	
Gender	: Pria / Wanita *	
Job	:	
Address	:	
Contact	:	

Note: The first two boxes in the initials are filled in with the first two letters of the two words of the name, and the third box is filled in with the date of birth. If the date of birth contains two numbers, use only one of them.

Example: Name: [name], Date of Birth: Januari 8th → [L|C|8].

MEDICAL HISTORY

History	Yes	No	Unknown
Have you ever had anaemia within the last 5 years?			
Do you have a history of kidney disorder?			
Do you have a history of stomach ulcers or GERD?			
Do you have a history of liver disorder?			
Are you an active smoker < 5 years?			
Are there any family members who smoke?			
Are you undergoing any medical treatment? Please specify!			

Signature of officer after filling out form:

Initials:

Date:

SAMPEL

Research Number:	Respondent's initials: []
------------------	---

SCREENING 2 – ANTHROPOMETRY AND BLOOD PRESSURE

ANTHROPOMETRIC EXAMINATION (PRE)	
Body weight : kg	Body height : cm
BMI : kg/m ²	
Waist Circumference: cm	
BLOOD PRESSURE MEASUREMENT (PRE)	
Blood pressure:	

ANTHROPOMETRIC EXAMINATION (POST)	
Body weight : kg	Body height : cm
BMI : kg/m ²	
Waist Circumference: cm	
BLOOD PRESSURE MEASUREMENT (POST)	
Blood pressure:	

Signature of officer after filling out form: Initials: Date:

SAMPEL

Research Number:	Respondent's initials: []
------------------	----------------------------

SCREENING 3 – BLOOD AND BIOCHEMICAL TESTS

a. Initial Screening

Parameters	Test Date/Time	Result	Status
Hematology Profile	[] / [] / [] (DD/MM/YY) [] . [] WIB	RBC : $10^6/\mu\text{L}$ HB : g/dL HCT : % MCV : fL MCH : pg	 Eligible  Not Eligible
Lipid Profile	[] / [] / [] (DD/MM/YY) [] . [] WIB	TC : mmol/L HDL : mmol/L LDL : mmol/L Tg : mmol/L	 Eligible  Not Eligible
Fasting Blood Glucose	[] / [] / [] (DD/MM/YY) [] . [] WIB	mmol/L	 Eligible  Not Eligible
ALT	[] / [] / [] (DD/MM/YY) [] . [] WIB	$\mu\text{kat/L}$	 Eligible  Not Eligible

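### Either arm may be used for blood pressure at each visit and the form does not record which, so avoidable noise can enter the paired change; the value analysed from three readings is also undefined

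*Combined protocol and SAP*

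**What the plan says.** All references are to the combined protocol and SAP.

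- **Arm.** Section 7.8, step d: "The sphygmomanometer is placed on the right or left arm approximately 3 cm above the elbow crease". No section asks for the same arm at both visits.
- **Readings.** Section 7.8, step e: "Blood pressure measurements will be taken three times, with a 1-minute interval between each measurement".
- **Recording.** Section 7.8, step f: "The systolic and diastolic pressure results are recorded". It does not say whether this means all three readings, their mean, or one of them.
- **Form.** In Appendix 1, Screening 2, the blocks that begin "BLOOD PRESSURE MEASUREMENT (PRE" and "BLOOD PRESSURE MEASUREMENT (POST" each hold one open line for blood pressure. Neither has a field for the arm, for separate readings or for a mean.
- **Role of the outcome.** Section 3.2, objective 1, assesses the effect of white tea "based on body weight, body mass index (BMI), waist circumference, and blood pressure". Section 7.5 sets the two measurement days as day 0 and day 15.
- **Analysis.** Section 8 compares before with after by t-test or Wilcoxon test. Its opening line, "The mean data before and after treatment will be tested for homogeneity and normality", concerns the before and after data sets and gives no rule for reducing three readings to one value per visit.

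**The concern.** The study has no control group, so the within-person change from day 0 to day 15 is the only evidence on blood pressure. Anything that differs between a subject's two visits, other than the tea, goes straight into that change. Step d leaves the arm free at each visit. If the arm differs between visits, the subject's own between-arm difference is added to or subtracted from the change. Because the arm is not recorded, an analyst can neither adjust for it nor find out how often it happened.

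The three readings are a second, separate matter. Averaging them would reduce reading error at no cost, but the plan does not say that the average is what is recorded or analysed. With no rule, staff may keep one reading, and may choose which. At stake is the precision of one outcome in objective 1 and some unneeded discretion over the value kept.

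**Working it through.** **The plan's own figure.** The documents give no SD, precision or power for blood pressure. The only related number is the sample size in Section 6: 15 / (1 − 0.20) = 18.75, rounded up to 19. It reproduces. It comes from a rule of thumb and not from blood pressure, so nothing below changes it.

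**Model.** Let s be the SD of a single reading within a visit, v the SD of the true change between visits, a the SD of the within-person difference between arms (taken as centred on zero), and q the share of subjects whose arm changes. All four are assumptions, in mmHg except q.

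- One reading per visit, same arm: Var(change) = 2s² + v²
- Mean of three per visit, same arm: Var(change) = 2s²/3 + v²
- Arm free: add q·a² to either

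Reading errors are treated as independent within a visit. If v is built from a between-visit SD b at each visit, then v² = 2b².

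**Step 1: arm term alone, mean of three already used.** With a = 4 and q = 0.5, q·a² = 8.

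- s = 6, v = 5: same arm 24 + 25 = 49; arm free 57; ratio 57/49 = 1.16 (SD 7.0 to 7.5)
- s = 6, v = 7: same arm 24 + 49 = 73; arm free 81; ratio 81/73 = 1.11 (SD 8.5 to 9.0)

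More extreme inputs widen this:

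- a = 3, q = 0.25, b = 8, s = 6: (152 + 2.25)/152 = 1.01
- a = 5, q = 0.5, b = 4, s = 3: (38 + 12.5)/38 = 1.33

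**Step 2: one reading kept instead of the mean of three, same arm.**

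| s | v² | One reading | Mean of three | Ratio |
|---|---|---|---|---|
| 3 | 128 (b = 8) | 18 + 128 = 146 | 6 + 128 = 134 | 1.09 |
| 4 | 72 (b = 6) | 32 + 72 = 104 | 10.7 + 72 = 82.7 | 1.26 |
| 4 | 49 (v = 7) | 32 + 49 = 81 | 10.7 + 49 = 59.7 | 1.36 |
| 6 | 49 (v = 7) | 72 + 49 = 121 | 24 + 49 = 73 | 1.66 |
| 6 | 25 (v = 5) | 72 + 25 = 97 | 24 + 25 = 49 | 1.98 |
| 8 | 25 (v = 5) | 128 + 25 = 153 | 42.7 + 25 = 67.7 | 2.26 |

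The ratio runs from about 1.1, where day-to-day variation dominates, to about 2.3, where reading error dominates. If the mean is what staff write down, the ratio is 1.0.

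**Step 3: a middle case for power.** Take b = 6, s = 4, a = 5, q = 0.5, with 15 completers, a two-sided 5% paired t-test and an illustrative 5 mmHg change.

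- One reading, arm free: variance 104 + 12.5 = 116.5, SD 10.8, power 39%
- One reading, same arm: variance 104, SD 10.2, power 42%
- Mean of three, same arm: variance 82.7, SD 9.1, power 51%

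**The case against.** A reader might infer that the precision of the three readings is lost because analysts cannot average what the form does not hold. The documents do not support that. The line on the form is open and could hold the mean or all three readings. Section 10.3 says that all research data obtained go onto the screening form. Section 9.2 requires source documents to be kept, and Section 10.1 promises standard operating procedures. This part of the objection stands: what is missing is a rule for the analysed value, and a loss is possible but not shown.

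A reader might also infer that free choice of arm biases the result. It does so only if switching is systematic, for example if most subjects move from one arm to the other in the same direction. Nothing in the plan suggests that, and nothing says staff will switch at all. Otherwise switching adds noise, and only for those who switch.

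The sizes rest wholly on assumed SDs, and correlated errors between readings a minute apart would shrink the gain from averaging. Blood pressure is also one of many outcomes in a pilot with no named primary outcome. All of this is fair and limits the weight of the point.

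It does not remove the arm problem. The general provisions on forms, source documents and procedures can preserve only what is collected, and no section asks anyone to note the arm.

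**Conclusion.** The point holds as a minor, free improvement. Its firm part is the arm. Step d permits a different arm at each visit and the form does not capture it, so any resulting noise in the paired change is avoidable beforehand and not correctable afterwards. If the mean of three is already used, the variance of the change is about 1.1 to 1.2 times as large, assuming an arm-difference SD of 4 mmHg, half of subjects switching, a reading SD of 6 mmHg and an SD of true change of 5 to 7 mmHg. If no one switches arms, there is no cost.

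The readings are a conditional part. If a single reading is kept, the variance is about 1.1 to 2.3 times that of the mean of three, over reading SDs of 3 to 8 mmHg and the true-change SDs shown. If the mean is recorded, nothing is lost. The documents do not say which applies.

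The sample size of 19 is unaffected, and the plan's conclusions on other outcomes do not depend on this.

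**What to change.** - In Section 7.8, step d, require the same arm on day 0 and day 15, and add an arm field to both blood pressure blocks of Screening 2.
- In the same blocks, replace the single line with three systolic and three diastolic fields per visit.
- In Section 7.8 or Section 8, state that the analysed value is the mean of the three readings, for systolic and diastolic separately.

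The cost is a form edit and two sentences. No visit, subject or reading is added. If day 0 measurements have already been taken, ask staff whether the arm and the separate readings can be recovered from source documents, and report how many subjects have them.

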7.9. Hematology Profile Measurement

Haematological analysis will be conducted at the clinical laboratory of the Bandung District Health Office. Blood samples were collected on day 0 (one day before the intervention) and day 15 (one day after the last day of the white tea intervention). The samples were stored in EDTA tubes and analyzed using an Erba H360 automatic haematology analyzer.

7.10. Biochemical Measurement

The investigation involved the performance of a comprehensive array of analytical procedures, including lipid profile, blood glucose, blood urea nitrogen, serum creatinine, ALT and AST tests. These were conducted at the Bandung District Health Office clinical laboratory, employing the utilisation of a Cobas C 311 biochemical automatic analyzer.

7.11. estimated Glomerular Filtration Rate Value Measurement

The creatinine level obtained will be used to calculate the eGFR value. The eGFR value will be calculated using an online calculator based on creatinine level, age, and gender. (<https://kidney.org.au/health-professionals/egfr-calculator>).

7.12. Antioxidant Enzymes Analysis

Antioxidant enzyme activity testing will be conducted at the Biomedical Laboratory, Faculty of Medicine, Padjadjaran University. Enzyme activity analysis will be performed on human blood serum collected on days 0 and 15. The analysis of antioxidant enzyme activity encompasses the assessment of superoxide dismutase (SOD), catalase (CAT) and glutathione peroxidase (GPx) activity. The analysis procedure will refer to the manual guideline in the Elabscience KIT.

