1. PROTOCOL RESUME

1.1. Protocol Resume

Protocol title:

Effect of White Tea (*Camellia sinensis* L.) Beverages on Anthropometric, Hematological, Biochemical and First Line Antioxidant Enzymes Activity of Healthy Human (Superoxide Dismutase, Catalase, and Glutathione Peroxidase)

Research aims:

Understanding the potential of white tea for human health in terms of anthropometry (body weight, body mass index and waist circumference), blood pressure and biochemistry (lipid profile, blood glucose levels and antioxidant enzyme activity). Furthermore, the safety of white tea products will be evaluated by means of haematological parameters (red blood cells, haematocrit, haemoglobin, mean corpuscular volume (MCV), and mean corpuscular haemoglobin (MCH)), liver parameters (alanine aminotransferase (ALT) and aspartate aminotransferase (AST)), and renal parameters (creatinine levels, estimated glomerular filtration rate (eGFR), and blood urea nitrogen) following a 14-day period of white tea consumption.

Study design:

This study will combine a pilot study with a pre-post quasi-experimental design.

Specific aims

1. Determine the effect of white tea consumption on the anthropometry of healthy subjects based on body weight, body mass index, waist circumference, and blood pressure.
2. Determine the effect of white tea consumption on the biochemical parameters of healthy subjects based on blood glucose, lipid profile (total cholesterol, low-density lipoprotein (LDL), high-density lipoprotein (HDL), and triglycerides), alanine aminotransferase (ALT), aspartate aminotransferase (AST), serum creatinine levels, estimated glomerular filtration rate (eGFR), and urea nitrogen levels.
3. Determine the effect of white tea consumption on blood parameters in healthy subjects based on red blood cell count, haemoglobin, haematocrit, mean corpuscular haemoglobin (MCH), and mean corpuscular volume (MCV).
4. Determine the effect of white tea consumption on the activity of first-line antioxidant enzymes (superoxide dismutase, catalase, and glutathione peroxidase) in healthy subjects.

Pre-post quasi-experimental study design

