All data pertaining to the study will be stored on CRFs/individual screening sheets. The data will be recorded in both soft and hard file formats on a daily basis.

Evaluation Criteria

Anthropometric measurements, blood pressure, haematology, and biochemistry tests will be conducted before the intervention and one day after the last intervention (day 0 and day 15). Anthropometric measurements, blood pressure, and blood sampling will be conducted at the Faculty of Pharmacy, Padjadjaran University. The biochemical examinations will be carried out at the clinical laboratory of the Bandung City Health Office, while the complete haematology and antioxidant enzyme examinations will be carried out at the Biomedical Laboratory of the Faculty of Medicine, Padjadjaran University. The results of the examinations conducted before and after the white tea intervention will be analyzed to ascertain the effect of white tea consumption over a period of 14 days. The types of food and beverages consumed by the research subjects and their daily activities were recorded in the CRF for a period of 28 days (from the wash-out phase to the observational phase).

Statistical Analysis

The effect of white tea administration will be compared before and after treatment using a t-test analysis.

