4. STUDY DESIGN

The present study adopts a quasi-experimental design, conducted as a pilot study, with the objective of ascertaining the effect of white tea consumption on several human health parameters. These parameters include anthropometry, blood pressure, haematology, biochemistry, and antioxidant enzyme activity. The study is divided into three stages. Firstly, a washout stage is conducted over the first seven days. This is followed by an intervention/treatment stage for 14 days, which is conducted one day after blood sampling. Finally, an observation stage is conducted for the last seven days to ensure that the subjects are in good condition after the intervention.

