6. TARGET POPULATION AND SAMPLE SIZE

The population utilised in this study comprised healthy subjects residing at Padjadjaran University and its environs who had completed the recruitment form on Google Forms. The respondents' data that had been entered underwent preliminary screening based on the following inclusion and exclusion criteria.

Inclusion criteria

- a. Participants are members of the Padjadjaran University community and surrounding areas aged 20-35 years (excluding women who were either unmarried or sexually inactive).
- b. Participants must not have been smokers for less than 5 years.
- c. Participants must not have a history of anaemia, liver or kidney disease.

Exclusion criteria

- a. Participants were required to take certain medications or vitamin supplements.
- b. The subjects reported experiencing discomfort during the administration of the product.
- c. Prior to the initiation of treatment, biochemical results were found to be outside the normal range.

This study utilised a pilot study, and the minimum sample size calculation was performed using the thumb method with a non-central t-distribution (NCT) approach. Whitehead stated that the minimum sample size for a power (β) value of 90% and a significance (α) value of 5% is 15 for each group. Considering a 20% possibility of dropouts, we used 19 subjects in the study. The following table provides a reference for the calculation of the sample size, as outlined by Whitehead et al. (2016) (27).

Table 8. Estimated stepped rules of thumb for required pilot trial sample size per treatment arm when the NCT approach will be used to calculate the main trial sample size.

Standardised difference	80% powered main trial	90% powered main trial
Extra small ($\delta < 0.1$)	50	75
Small ($0.1 \leq \delta < 0.3$)	20	25
Medium ($0.3 \leq \delta < 0.7$)	10	15
Large ($\delta \geq 0.7$)	10	10

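### Section 7.12 does not require each subject's day-0 and day-15 enzyme samples to be assayed together, and the screening form points to separate runs, so assay drift could pass for an effect of tea

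*Combined protocol and SAP*

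**What the plan says.** On the assay, section 7.12 names the laboratory, the three enzymes and the sampling days: "Enzyme activity analysis will be performed on human blood serum collected on days 0 and 15". For procedure it adds only: "The analysis procedure will refer to the manual guideline in the Elabscience KIT". It gives no rule on freezing, batching, kit lot, control samples or same-run assay, and no other section supplies one.

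On timing, section 4 describes the treatment stage as one "which is conducted one day after blood sampling". The Evaluation Criteria in section 1.1 describe examinations made before and after the intervention. In Appendix 1, Screening 3, the Initial Screening table has a row for SOD, CAT and GPx with its own test date and time and an Eligible / Not Eligible box. The Final Screening table repeats that row, box included.

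On eligibility, the aims in section 1.1 group the enzymes under "biochemistry (lipid profile, blood glucose levels and antioxidant enzyme activity", and exclusion (c) in section 6 reads "Prior to the initiation of treatment, biochemical results were found to be outside the normal range". The baseline withdrawal rule in section 7.5 lists different tests: "Should the preliminary investigative results pertaining to haematological parameters (RBC, HB, HCT, MCV and MCH), ALT, AST, serum creatinine levels, eLFG and urea nitrogen levels". The enzymes are not among them.

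On design and analysis, section 1.1 states "This study will combine a pilot study with a pre-post quasi-experimental design" and "The effect of white tea administration will be compared before and after treatment using a t-test analysis". Section 8 adds a Wilcoxon test for non-normal data. Neither analysis has a term for assay run.

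**The concern.** An eligibility decision needs a result before treatment. If staff complete the Initial Screening form as it stands, day-0 enzymes are assayed before the first cup of tea, about two weeks before any day-15 serum exists. The two time points would then fall in different runs and perhaps different kit lots.

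A difference in level between those runs moves every subject's change in the same direction. A concurrent control group would reveal it, but this trial has none. A paired t-test or Wilcoxon test sees only the change and attributes it to tea. Extra subjects do not help, because they narrow the standard error around the shifted value.

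SOD, CAT and GPx are in the study title and form the fourth specific aim. Section 1.2 makes further development of the product depend partly on an increase in their activity.

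**Working it through.** **The plan's own figure.** Section 6 takes 15 subjects and allows for 20% dropout: 15 / (1 − 0.20) = 18.75, rounded up to 19. This reproduces. The checks below use 15 completers, with 19 as the case of no dropout.

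**Do the documents separate the runs?**
- Pointing to separate runs: the enzyme row on the Initial Screening form with its own test date and eligibility box; tea starting one day after sampling; the Evaluation Criteria's before-and-after examinations; and the aims counting enzymes as biochemistry, which exclusion (c) uses.
- Pointing the other way: section 7.12 gives collection days only; the section 7.5 list omits the enzymes; and the same box appears in Final Screening, where eligibility has no meaning.

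Separate runs are therefore a reasonable inference that no section states. That same-run assay is not required is plain from the text.

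**Effect of a fixed shift.** Suppose tea has no effect and all day-15 results move by d standard deviations of the paired difference. The two-sided 5% paired t-test then follows a non-central t with n − 1 degrees of freedom and non-centrality d√n. (The documents do not state sidedness; two-sided is assumed.)

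| Shift d | Rejects, n = 15 | Rejects, n = 19 |
|---|---|---|
| 0.1 | 6.5% | 7.0% |
| 0.2 | 11.2% | 13.1% |
| 0.3 | 19.2% | 23.6% |
| 0.5 | 43.8% | 54.1% |

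**Effect of a random run shift.** The documents give neither a between-run CV nor an SD of change, so both are assumed, as percentages of the mean. With one run per time point and independent run effects, the shift has variance 2·CV². The mean change then has variance SD²/n + 2·CV², while the test uses SD²/n. The rejection rate with no tea effect is

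2·P(T > t_crit / √(1 + 2n·CV²/SD²)), with T on n − 1 degrees of freedom.

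For n = 15, CV 5%, SD 15%: t_crit = 2.145; 2 × 15 × 25 / 225 = 3.333; √4.333 = 2.082; 2.145 / 2.082 = 1.030; two-sided probability on 14 degrees of freedom = 0.32.

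| SD of change | CV 3% | CV 5% | CV 10% |
|---|---|---|---|
| 15%, n = 15 | 17% | 32% | 58% |
| 30%, n = 15 | 8% | 14% | 32% |
| 15%, n = 19 | 20% | 37% | 63% |
| 30%, n = 19 | 9% | 16% | 37% |

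These rates are per enzyme, and there are three.

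**Several cohorts.** If the 15 subjects start in three equal cohorts, each with its own pair of runs, the shifts partly average out and the spread between cohorts widens the estimated SD. By simulation, the CV 5%, SD 15% case falls from 32% to about 14%, and the 8% to 58% range becomes about 6% to 27%. With five cohorts the same case gives about 9%.

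**Same-run assay.** A level shift shared by both of a subject's samples cancels in the difference, so the rejection rate due to run drift returns to 5% and N = 19 is unaffected.

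**The case against.** A reader might infer that the form forces separate runs. The documents do not support that. Every test in the Final Screening table carries the same box after treatment, so it may be a copied template column. The enzymes have no units on the form and no normal range anywhere, so the box could hardly be applied. Section 7.5 leaves them out of baseline withdrawal. The Evaluation Criteria list biochemical and enzyme examinations separately, at different laboratories, and section 7.10 gives the biochemistry panel without enzymes. If no decision rests on the day-0 enzyme result, nothing requires it early. This argument stands, and separate runs must be described as indicated and not as stated.

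The kit manual, or the operating procedures promised in section 10.1, may set run controls and storage. That is possible, but neither is in the documents, and the comparison depends on the rule enough for section 7.12 to state it.

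The percentages rest on assumed inputs and on one run per time point. That also stands: no common start date is given, and staggered cohorts lower the figures.

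Finally, same-run assay leaves day-0 serum stored longer, which could itself move results in one direction, and it does nothing about dietary restriction, time trend or regression to the mean. Both are true. The first can be limited by keeping to the kit's stability limits; the second does not justify leaving in a bias that is easily removed.

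**Conclusion.** The point holds as a gap in section 7.12, with a form that points the wrong way. The protocol does not require paired enzyme samples to be assayed together, and in an uncontrolled before-after comparison neither planned test can separate a common run shift from an effect of tea. The direction of such a shift cannot be predicted.

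The size is conditional. With 15 completers, one run per time point, CV 3% to 10% and SD of change 15% to 30%, the false-positive rate per enzyme is 8% to 58% against a nominal 5%, with 32% at CV 5% and SD 15%. All of these inputs except the 15 are assumptions. None of this shows that separate runs are planned or that drift will occur. It is worth settling before any assay is run, because when all subjects share one run per time point, the analysis cannot later separate the shift from the effect of tea.

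**What to change.** In section 7.12, state that serum from both time points is frozen under the same conditions and that each subject's day-0 and day-15 samples are assayed in the same run with the same kit lot. In Appendix 1, remove the eligibility box against the enzymes on the Initial Screening form, or reconcile it with section 7.5, which does not use them. If a day-0 enzyme result is needed before treatment after all, keep an aliquot and assay it again beside the day-15 sample.

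The cost is one sentence and one form edit, with no extra subjects or blood draws; a repeat assay would arise only in the last case. The downside is about two more weeks of storage for day-0 serum, so section 7.12 should also require storage to stay within the stability limits in the kit manual.
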